4.2. Experimental design

4.2.1. Study plan

This is a randomized, multicenter, double-blind, placebo-controlled, parallel-group doseranging study which will be conducted in study centers in Russian Federation.

The study will consist of 3 periods: selection period up to 2 weeks, double-blind treatment period for 12 weeks + Follow up period for 2 weeks after double-blind treatment stop. The study plan is shown in Figure 1.

Figure 1. Study plan

Study periods Selection Period Double-blind Follow-Up treatment period (luseogliflozin or placebo) ASSE W-2W4**W8** W14 $\mathbf{W0}$ W12 $(\pm 3 \text{ days})$ (-14 days max) $(\pm 3 \text{ days})$ $(\pm 3 \text{ days})$ $(\pm 3 \text{ days})$ $\mathbf{D0}$ Selection Inclusion End of IMP **EoS** Randomization

Ongoing treatment with metformin

	No IMP	Luse	ogliflozin 2,5 mg gro	up (n=80)		No IMP
	No IMP	Luse	eogliflozin 5 mg grou	p (n=80)		No IMP
	No IMP	Luse	eogliflozin 10 mg grou	up (n=80)		No IMP
	No IMP		Placebo group (n=80)			No IMP
ASSE		W0	W4	W8	W12	W14

Selection period will precede the inclusion into the study once the informed consent is signed and will last 7- 14 days before the randomization into the study to confirm the eligibility of the patients. Treatment with metformin in stable (during the previous 3 months) dose should be continued, the dosage frequency of metformin should be also unchanged. Diet and physical activity as routinely advised to the diabetic patients should be followed.

At inclusion visit the eligible patients will be randomized to receive either 2.5 mg, 5 mg, 10 mg Luseogliflozin or placebo in 1:1:1:1 manner. Randomization will be stratified on HbA1c (< 8.5% and $\ge 8.5\%$) and center (stratum 'center performing PK sampling' and another one 'center not performing PK sampling').

The patients will start Luseogliflozin and/or placebo next day after inclusion visit in addition to the ongoing treatment with metformin.

After randomization the patients will undergo 4 study visits: Week 4 (W4), Week 8 (W8), Week 12 (W12) visits and the End of Study (EoS) follow up visit in 2 weeks after double-blind treatment stop (W14).

During the double-blind treatment the doses of luseogliflozin and metformin as well as dosage frequency of metformin should not be changed unless for safety reasons (e.g. hypoglycaemia); antidiabetic medications other than metformin are not allowed during the selection period and double-blind treatment period, except in case of rescue therapy (see section 6.3.1).

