4.3. Measures to minimise bias

The randomised design is one of the main aspects which helps to minimise bias. The important aspect of this study design is that the patients are randomly assigned to the study groups that help in avoiding bias in patient allocation-to-treatment that a physician might be subject to. Stratification of randomization on baseline HbA1c and centre will be used.

It also increases the probability that the differences between the groups can be attributed only to the study treatment. Therefore, in this particular study this design will help to evaluate effectiveness and safety of different dose regimes.

Bias is avoided not only by randomization but also by blinding. This study is double blind, which means that neither patient nor investigator knows to which treatment the patient has been assigned.

Randomization list will be generated by a dedicated unblinded biostatistician using the unique randomization seed number to ensure reproducibility of results. Randomization list will be shared with the unblinded parties only (as listed in the communication plan for the study). Randomization list will be shared with the blinded statistician only at the stage of final analysis after the database is fully locked.

Group allocation will be concealed from the site staff and all blinded staff as randomization codes will not have any direct relation to any group allocation (i.e. this can be figured out only if the randomization list is available). Thus, all information sources (source documents,

laboratory reports, PK reports, eCRF, etc.) will store only the patients number as study participant identifier.

Treatment randomization and allocation will be centralised by Interactive Response System (IRS). The structure responsible for designing and constructing the randomization lists in blind will be the CRO.

Test drug (luseogliflozin) and placebo will have the same appearance. As the tablet size of luseogliflozin 2.5 mg is smaller than tablet of luseogliflozin 5 mg, 1 tablet (luseogliflozin 2.5 mg or placebo depending on the group) has been added to each arm to maintain the blind.

The primary efficacy variable (HbA1c) will be measured by a central laboratory in order to centralize and harmonise the data.

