10. STATISTICS

10.1. Statistical analysis

This section briefly describes the planned statistical analysis. Details for the analysis will be provided in the separate statistical analysis plan (SAP) that should be finalized before the database lock.

Descriptive statistics:

- all quantitative data will be presented as number of valid observations, mean, 95%confidence interval (CI) for mean, standard deviation, median, min/max and 25th and 75th percentiles.
- all qualitative data will be presented as number of valid cases, number of cases for each response category, percentage of response category relative to the number of valid cases and exact Clopper-Pearson binomial confidence interval for proportion for each category.

Assessment of normality for the quantitative data will be performed using the Shapiro-Wilk test.

Disposition of study participants:

Disposition of study participants will be provided as follows:

- Number of screened patients (total)
- Screening failures (tabulated by reasons)
- Randomized patients by group
- Early terminated patients (tabulated by reasons)
- Study completers by group
- Allocation of patients to FAS and PPS populations

Baseline characteristics will be presented by group:

- Demographics (age, gender);
- Anthropometry (weight, height, BMI);
- Baseline laboratory data;
- Medical history and concomitant conditions;
- Prior and concomitant medications.

Efficacy analysis:

In order to meet the primary objective of the study, the efficacy of at least one dose of luseogliflozin as compared to placebo after 12 weeks of treatment in glycaemic control will be assessed from the change from baseline to W12 in HbA1c, in patients of the RS. Analysis of covariance (ANCOVA) will be used as the main method of assessment of the primary endpoint, with baseline (W0) HbA1c value being a covariate.

Unrestricted least significant differences (LSD) method will be applied to the ANCOVA results with the calculation of least-square (LS) means with 95% CI for LS means for the difference between each dose level and placebo.

Finally, to assess the dose-response of the investigation product with regards to the primary endpoint, contrasts will be build based on the ANCOVA results.

Before performing ANCOVA, a multiple imputation procedure will be used to impute:

- Missing data for the primary endpoint at 12 week (for patients with missing data at W8 and W12 and for patients with missing data at W12 only)

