- Data collected after rescue therapy for non-controlled patients.

This approach allow to evaluate, as primary analysis, the hypothetical « proper effect » of luseogliflozin without additional effect of rescue therapy.

These analysis on primary endpoint will be done in the Randomised set (RS) and – additionally – in the per protocol set (PPS). Any differences between the results in RS and PPS will be investigated and explained, yet, RS will serve as the main analysis set at all times.

Two additional analysis will be performed on the primary endpoint on RS and PPS:

- Before performing ANCOVA, a multiple imputation procedure will be used to impute missing data for the primary endpoint at 12 weeks. Here data collected after rescue therapy will be taken into account in the analysis allowing to evaluate the effect of "treatment policy" of luseogliflozin + rescue medication VS placebo + rescue medication.
- Last observation carried forward (LOCF) method will be used to impute post rescue evaluations and other missing data at 12 weeks for the primary endpoint (for a bridging objective with studies performed on Japanese population)

The multiple imputation approach will be based on the regression method to impute values for each missing data at W008 and W012. Covariate use for the regression method will be auxiliary variables which might be predictive of both the chance of missing values and the underlying values themselves. Those additional auxiliary variables will be defined, before the blind is broken, in the SAP.

Secondary efficacy parameters – the following parameters will be assessed:

- 1) Quantitative parameters:
- Change in fasting plasma glucose,

- Change in postprandial plasma glucose,
- Change in body weight,
- Change in waist circumference

These parameters will be assessed and tested in the same spirit of the primary parameter and precision will be given in the SAP.

- 2) Qualitative parameters:
- The proportion of patients with HbA1c<7%
- The proportion of patients with HbA1c<6.5%

These parameters will be compared between the groups using the logistic model, including the fixed, categorical effect of treatment as well as the continuous, fixed covariates of baseline HbA1c.

Precision will be given in the SAP

Safety analysis will be performed by group for the following parameters:

- Frequency of emergent adverse events;
- Frequency of serious adverse events / ERIN;
- Frequency of adverse events related to the IMP (adverse drug reactions);

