- Frequency of adverse events related to the conditions of the protocol;
- Frequency of any adverse events leading to treatment withdrawal;
- Frequency of all AE of Special Interest and frequency of each individual AEOSI;
- Laboratory parameters by visit;
- Frequency of laboratory parameter abnormalities by visit;
- Vital signs (HR, SBP, DBP) by visit;
- Frequency of vital signs (HR, SBP, DBP) abnormalities by visit;
- 12-lead ECG results by visit;
- Frequency of 12-lead ECG abnormalities by visit.

Frequency data will be compared between the groups using exact Fisher tests; numeric data will be compared between the groups using the t-test or Wilcoxon-Mann-Whitney test on ranks depending on the normality of the parameter distribution (which will be tested using Shapiro-Wilk test). Laboratory parameters, vital signs and 12-lead ECG data will be analysed using two-way ANOVA (or ANOVA on ranks, if the distribution is not meeting the normality criteria) to account for group and visit factors simultaneously.

Interim analysis

No interim analysis is planned for this study.

Study populations

- Randomized Set (RS):

All patients to whom a therapeutic unit was randomly assigned using IRS.

- Per Protocol Set (PPS):

All the patients of the RS that do not have any significant protocol deviations. List of deviations will be reviewed for the determination of their significance prior to the database lock and randomization list unblinding.

- Safety Set (SS):

All patients having taken at least one dose of study drug.

- **Pharmacokinetic set**: all patients for whom blood samples were collected with no deviations that might affect the pharmacokinetic interpretation

- **Pharmacokinetic/Pharmacodynamic set:** all included patients for whom blood samples and 24-hour urinary glucose measurements were collected with no deviations that might affect the PK and/or PD interpretations.

Significance level:

The type I error of the statistical tests will be set at 5% (two-sided situation).

Multiplicity issues:

In order to take into account the multiplicity of comparisons associated with the primary objective of the study (demonstration of superiority of at least one luseogliflozin dose as compared to placebo on the primary efficacy endpoint); a Bonferroni correction will be used for the primary analysis.

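### The stated ANCOVA and responder model leave out the PK / non-PK centre stratum used in randomisation: a small, nearly free alignment point

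*Protocol*

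**What the plan says.** Section 4.2.1 stratifies the 1:1:1:1 randomisation on two factors. One is HbA1c, cut at 8.5%. The other is "center (stratum 'center performing PK sampling' and another one 'center not performing PK sampling", which has two levels. Section 4.3 restates this more briefly: "Stratification of randomization on baseline HbA1c and centre will be used".

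Section 10.1, and the summary sheet in near-identical terms, makes ANCOVA on the change in HbA1c to Week 12 the "main method of assessment of the primary endpoint, with baseline (W0) HbA1c value being a covariate". No other covariate is named. The secondary quantitative endpoints are to be handled in the manner of the primary one, and "precision will be given in the SAP". The logistic model for HbA1c below 7% and below 6.5% is described as "including the fixed, categorical effect of treatment as well as the continuous, fixed covariates of baseline HbA1c". Section 10.1 opens with a general deferral: "Details for the analysis will be provided in the separate statistical analysis plan (SAP) that should be finalized before the database lock".

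**The concern.** Stratified allocation balances centre type across the four arms. A linear model that ignores a balanced prognostic factor still estimates the treatment difference without bias. However, it leaves the factor's variance in the residual, so the reported standard error exceeds the true sampling variability of the estimate. The test is then conservative, and some precision secured by the design goes unused.

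The HbA1c stratum is not the issue, because the continuous baseline value largely carries it. Centre type has no counterpart in any stated efficacy model. At stake is a little precision, and a primary model that matches the randomisation and is fixed before unblinding.

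**Working it through.** **Inputs from the protocol.** 80 patients per arm and 320 in total; true difference 0.6; SD 1.1; two-sided t-test; overall alpha 5% with Bonferroni for three comparisons, so 0.05/3 = 0.0167 each (Sections 10.1 and 10.2). About 18 PK/PD patients per dose group (Section 9.2). The protocol gives neither a centre-type effect on HbA1c nor the share of patients at PK centres; both are assumed below.

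**Stated power.** SE of a dose-placebo difference = 1.1 × √(2/80) = 0.1739. At alpha 0.0167 the power is 0.847 (noncentral t, 158 df), 0.851 (316 df) or 0.854 (normal approximation). The stated figure of around 85% is reproduced from a plain t-test, so it does not rely on a stratum term.

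**ANCOVA.** Let f be the share of patients at PK centres and g the difference in mean HbA1c change between centre types. The stratum's share of variance is R² = f(1−f)g²/1.1², and omitting it inflates the SE by 1/√(1−R²) − 1. For f, 18/80 = 22.5% is the value if PK centres enrolled only subset patients; 50% maximises f(1−f).

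| g (assumed) | f = 22.5% | f = 50% |
|---|---|---|
| 0.1 | R² 0.14%, SE +0.07% | R² 0.21%, SE +0.10% |
| 0.2 | R² 0.58%, SE +0.29% | R² 0.83%, SE +0.42% |
| 0.3 | R² 1.30%, SE +0.65% | R² 1.86%, SE +0.94% |
| 0.5 | R² 3.60%, SE +1.85% | R² 5.17%, SE +2.69% |

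Example: 0.5 × 0.5 × 0.3² / 1.21 = 0.0186, and 1/√(1 − 0.0186) − 1 = 0.94%. These figures use 1.1 as the residual SD. To the extent that baseline HbA1c removes residual variance, the stratum's share rises in proportion.

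**Power with the term included** (SE = 0.1739 × √(1−R²)):

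| R² | SE | Power |
|---|---|---|
| 0 | 0.1739 | 0.847 |
| 0.5% | 0.1735 | 0.849 |
| 1% | 0.1731 | 0.851 |
| 2% | 0.1722 | 0.855 |
| 5% | 0.1695 | 0.867 |

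For g of 0.1 to 0.3, R² stays below 2%, so the gain is at most 0.855 − 0.847 = 0.008, under one point. The model as stated has 320 − 5 = 315 residual df (four arms plus baseline); adding centre type leaves 314.

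**Type I error.** 20,000 simulated trials, four arms of 80, stratum exactly balanced, total SD 1.1, treatment-only model without a baseline covariate:

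| Centre effect g, PK share f | Per comparison (nominal 0.0167) | Family-wise (limit 0.05) |
|---|---|---|
| 0, 30% | 0.0167 | 0.044 |
| 0.3, 30% | 0.0162 | 0.042 |
| 0.5, 50% | 0.0144 | 0.037 |

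Monte Carlo error is about √(0.0167 × 0.9833 / 20,000) = 0.0009 per comparison, so the shift at 0.3 points is within noise taken alone. With the stratum in the model, the same simulated data give 0.0168 to 0.0169.

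**Responder model.** Assume responder rates of about 20% and 38%, 80 per arm, half the patients at PK centres, and no baseline covariate. With a stratum log odds ratio of 0.3, adding the stratum moves the SE of the treatment log odds ratio from 0.3628 to 0.3637 and the z statistic from 2.470 to 2.475. With 1.0, the SE moves from 0.358 to 0.368 and z from 2.392 to 2.446. The SE rises, but the estimate moves further from zero (at 1.0, from 2.392 × 0.358 = 0.86 to 0.90), so z gains slightly.

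**The case against.** The strongest objection is that this is detail for the SAP, which was not available for this review. Section 10.1 calls itself brief, defers details, and does not say that baseline HbA1c is the only covariate. The SAP may already add centre type. That stands as a reason to keep the point small. It does not dispose of it: the protocol names the covariate in the summary sheet and again in Section 10.1, and lists the terms of the logistic model. It expressly leaves the auxiliary variables of the imputation to the SAP, but not the primary model's covariates.

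It also stands that centre type may not be prognostic. The factor is defined only by PK sampling, HbA1c is measured centrally for everyone, and the hospital stay of at least 24 hours at Week 4 concerns only the PK/PD subset. With no centre effect there is no gain and one degree of freedom is spent.

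A reader might infer more than the protocol supports:
- That standard errors are too large in both models. This holds only for the ANCOVA, and only if centre type is prognostic. In the logistic model, adjustment raises the SE of the log odds ratio.
- That the sample size or error control is faulty. The stated power is reproduced without the term, and the simulated error stays at or below nominal.
- That Sections 4.2.1 and 4.3 describe different designs, the second stratifying on each of the 36 centres. Section 4.3 reads more naturally as shorthand for the definition in Section 4.2.1. It needs a clarification and is not evidence of a contradiction.

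**Conclusion.** The point holds as a minor mismatch between randomisation and analysis: centre type is a stratification factor and is absent from the efficacy models as stated. For the primary ANCOVA the consequence is conditional and small: SE inflation of about 0.1% to 0.9% for assumed centre differences of 0.1 to 0.3 HbA1c points, and at most 2.7% for an assumed 0.5 points. The error is on the conservative side. The treatment estimate is not biased, type I error is not inflated, and the stated power of around 85% is unaffected. These sizes rest on assumed centre effects, PK-centre shares and responder rates, since the protocol gives none. The case for change is that the improvement is nearly free; the analysis as stated is not invalid.

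**What to change.** - In Section 10.1 and the summary sheet, state the primary ANCOVA with treatment, centre type (PK / non-PK) and continuous W0 HbA1c.
- Use the same terms in the secondary ANCOVAs, each with its own baseline value where the SAP specifies one, and in the two logistic models. In the logistic models the benefit to expect is in the test statistic.
- In Section 4.3, state that centre means the two-level centre type defined in Section 4.2.1.

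The cost is a sentence in each place and one residual degree of freedom of about 315. Centre type is a randomisation stratum, so it is already recorded in the interactive response system and no new data are needed. The change should be made before unblinding.

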Efficacy analysis:

In order to take into account the multiplicity of comparisons induced by the assessment of three luseogliflozin doses versus placebo, a Bonferroni correction will be used.

Primary endpoint

In order to meet the primary objective of the study, the efficacy of at least one dose of luseogliflozin as compared to placebo after 12 weeks of treatment in glycemic control will be assessed from the change from baseline to W12 in HbA1c, in patients of the RS.

Analysis of covariance (ANCOVA) will be used as the main method of assessment of the primary endpoint, with baseline (W0) HbA1c value being a covariate.

Unrestricted least significant differences (LSD) method will be applied to the ANCOVA results with the calculation of least-square (LS) means with 95% CI for LS means for the difference between each dose level and placebo.

Name of the sponsor: JSC Servier	Individual Study Table Referring to Part of the Dossier	(For National Authority Use only)
Name of Finished Product:	Volume:	
Name of Active Ingredient: Luseogliflozin	Page:	

Finally, to assess the dose-response of the investigation product with regards to the primary endpoint, contrasts will be built based on the ANCOVA results.

Before performing ANCOVA, a multiple imputation procedure will be used to impute:

- Missing data for the primary endpoint at 12 week (for patients with missing data at W8 and W12 and for patients with missing data at W12 only)
- Data collected after rescue therapy for non-controlled patients

This approach allow to evaluate, as primary analysis, the hypothetical « proper effect » of luseogliflozin without additional effect of rescue therapy.

Two additional analysis will be performed on the primary endpoint:

- Before performing ANCOVA, a multiple imputation procedure will be used to impute missing data for the primary endpoint at 12 weeks. Here data collected after rescue therapy will be taken into account in the analysis allowing to evaluate the effect of "the treatment policy" of luseogliflozin + rescue medication *versus* placebo + rescue medication.
- Last observation carried forward (LOCF) method will be used to impute post rescue evaluations and other missing data at 12 weeks for the primary endpoint (for a bridging objective with studies performed on Japanese population)

Study patients (disposition, baseline characteristics and follow-up) and safety analysis: Descriptive statistics will be provided.

Sample size rationale:

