10.2. Determination of sample size

The determination of the sample size was performed considering the primary endpoint, the HbA1c.

It was estimated on the change from baseline at W12, for a difference objective between at least one dose of luseogliflozin and placebo, based on a two-sided Student's t-test for independent samples and using the Bonferroni correction in order to maintain the experiment wise type I error at 5% (bilateral situation).

About 80 patients per treatment group (320 overall) allow to conclude that at least one dose of luseogliflozin is superior to placebo with a power of around 85% if the true difference is 0.6% for a standard deviation of 1.1 %.

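### Unrestricted LSD with 95% CIs and a Bonferroni correction are both specified for the three primary dose-placebo contrasts, and the protocol does not reconcile them

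*Protocol*

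**What the plan says.** The efficacy part of Protocol section 10.1 describes the primary ANCOVA and continues: "Unrestricted least significant differences (LSD) method will be applied to the ANCOVA results with the calculation of least-square (LS) means with 95% CI" for the difference between each dose and placebo. The summary sheet carries the same instruction under the primary endpoint: "Unrestricted least significant differences (LSD) method will be applied to the ANCOVA results".

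Three other places name a different procedure for the same comparisons:

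- The summary sheet, opening its efficacy analysis, refers to the "multiplicity of comparisons induced by the assessment of three luseogliflozin doses versus placebo, a Bonferroni correction will be used".
- Section 10.1, under multiplicity, gives the primary objective as "demonstration of superiority of at least one luseogliflozin dose as compared to placebo on the primary efficacy endpoint" and says "a Bonferroni correction will be used for the primary analysis".
- Section 10.2 sizes the trial "using the Bonferroni correction in order to maintain the experiment wise type I error at 5% (bilateral situation").

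Section 10.1 carries the primary strategy for dose comparisons over to the secondary endpoints, with no adjustment across endpoints.

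**The concern.** LSD is a named pairwise comparison method. In its unrestricted form it omits the overall F-test as a gate and tests each pair at the full level. The 95% CI is the interval that goes with such a test. A Bonferroni test of three contrasts uses 0.05/3 per contrast, and the interval that agrees with it is 98.33%. The protocol does not state that interval level; it follows from the test.

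The trial succeeds if at least one dose beats placebo, so the verdict on each dose feeds straight into the trial's conclusion. As written, the report can show a primary 95% CI that excludes zero for a dose that fails the primary test, and the protocol does not say that the interval carries no claim. Because the secondary endpoints inherit the dose strategy, the same mismatch can arise there.

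**Working it through.** **Inputs.** From section 10.2: n = 80 per arm, difference 0.6, SD 1.1, two-sided t-test, Bonferroni, power around 85%. From section 4.2.1: allocation 1:1:1:1. One shared placebo arm of equal size gives a correlation of 0.5 between any two dose-placebo contrasts.

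**1. The plan's own power.** SE = 1.1 × √(2/80) = 0.174, and 0.6/0.174 = 3.45.

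| Two-sided level per dose | Critical z | Power, normal | Power, t (df 158) | n per arm for 85% |
|---|---|---|---|---|
| 0.05/3 = 0.0167 | 2.394 | Φ(3.45 − 2.394) = 85.4% | 84.7% | 80 |
| 0.05 | 1.960 | Φ(3.45 − 1.960) = 93.2% | 92.9% | 61 |

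With the pooled ANCOVA error (df = 320 − 5 = 315) the Bonferroni power is 85.1%. The stated 85% and the planned 80 per arm are reproduced at 0.05/3, not at 0.05.

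**2. Family-wise error with no true effect.** For critical value c and correlation 0.5,

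FWER = 1 − ∫ φ(u) [Φ(u + c√2) − Φ(u − c√2)]³ du.

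| Rule | Any two-sided rejection | False claim of benefit only |
|---|---|---|
| Each dose at 0.05 | 12.5% | 6.3% |
| Each dose at 0.05/3 | 4.4% to 4.5% | 2.2% |

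The t version (df 315) gives 12.5% and 4.4%. A simulation of 1,000,000 draws gives 12.5% for the unadjusted two-sided rule and supplies the last column. For comparison, three independent tests at 0.05 would give 14.3%, and the simple sum is 15%.

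**3. Where interval and test disagree.** With t quantiles, the half-width is 0.342 for a 95% CI and 0.419 for a 98.33% CI. The ratio is 0.419/0.342 = 1.22, so the matched interval is about 22% wider. An observed difference between about 0.34 and 0.42 in favour of a dose has a 95% CI excluding zero but p above 0.0167.

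**4. How often.** At a true difference of 0.6, the estimate for a given dose falls in that band with probability about 8%. For the trial-level conclusion of at least one dose, a Bonferroni success is always also an unadjusted success. The gap between the two success probabilities is therefore the chance of opposite verdicts:

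| Doses with a true 0.6 effect (others zero) | Unadjusted | Bonferroni | Gap |
|---|---|---|---|
| 1 | 93.1% | 85.4% | 7.7 points |
| 2 | 98.1% | 94.5% | 3.6 points |
| 3 | 99.2% | 97.1% | 2.1 points |

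**The case against.** The strongest reply is that the decision rule is stated, more than once, and it is Bonferroni. The multiplicity paragraph exists to answer this question, the summary sheet puts Bonferroni ahead of the LSD sentence, and the sample size is consistent only with it. On this view LSD merely describes how the pairwise differences and intervals come out of the ANCOVA, and Bonferroni sets the threshold. Reporting 95% CIs beside an adjusted test is a common convention, and section 10.1 leaves detail to the SAP. The general line "The type I error of the statistical tests will be set at 5% (two-sided situation") is no evidence of conflict either, because section 10.2 treats 5% as the experiment-wise level.

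Most of this stands. A reader might infer that the primary decision rule is open between two routes, or that the trial will run at 12.5% family-wise error. The documents support neither. No passage lets a primary claim rest on an unadjusted p-value or on a 95% CI, and the 12.5% arises only if every Bonferroni statement is set aside. It also counts false findings that the drug is worse than placebo. The 8% per dose is likewise not the risk to the overall conclusion, which is smaller when more than one dose works.

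What does not fall is the mismatch. The protocol positively names an unadjusted procedure and an interval level for the contrasts that it also places under Bonferroni. That is a statement on the page, not detail deferred to the SAP, and the reading that joins the two has to be supplied by the reader.

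**Conclusion.** The point holds as an unreconciled procedure label and interval level. Bonferroni is the evident governing rule; applied as such, it gives a family-wise error of about 4.4% and the power the protocol states. The 12.5% (6.3% in the favourable direction) is conditional on LSD or the 95% CIs being used for the claim.

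What remains under the intended rule is a band of observed differences, about 0.34 to 0.42, in which the reported primary interval and the primary test point in opposite directions. The band rests on SD 1.1, 80 analysed per arm and complete data; it scales with the standard error actually obtained from the ANCOVA after multiple imputation. The family-wise figures rest on equal arms with one shared placebo.

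**What to change.** Make these changes in section 10.1 and in the summary sheet, and carry them into the SAP before the blind is broken:

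1. Delete the unrestricted LSD label, or state that the pairwise ANCOVA p-values for each dose against placebo are compared with two-sided 0.05/3 = 0.0167.
2. State that only this test supports the primary claim.
3. Report 98.33% CIs for the three primary contrasts, or keep the 95% CIs and label them as unadjusted and descriptive.
4. Treat the dose comparisons for the secondary endpoints in the same way, since they inherit the strategy.

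The cost is wording only: sample size, data collection and conduct do not change. If matched intervals are chosen, they are about 22% wider than the 95% CIs.
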